6.5.3 Analyses of Clinical Exploratory Endpoint

6.5.3.1 Severity Score for acute allergic reactions

Severity scores during OFCs will be calculated based on the severity grading system for allergic reactions developed by Dribin and colleagues²⁴ and will be compared

between randomization groups using generalized mixed effects models.

6.6 Multiplicity Adjustment

There will be no formal correction of the Type I error rate for multiple testing of statistical hypotheses for any of the secondary clinical endpoints. Therefore, p-values generated from these secondary analyses should be treated as descriptive in nature.

The primary mechanistic objectives are to elucidate immune mechanisms induced by daily ingestion of sub-threshold amounts of peanut, and to identify biomarkers of and functional pathways underlying desensitization potential. We will test if peanut ingestion is associated with the following immune and transcriptomic processes:

- Suppression of serum peanut-specific IgE
- Increase in serum peanut-specific IgG and IgG4
- Change in peanut IgE and IgG4 epitope binding scores
- Decrease in basophil activation tests
- Decrease in peanut-specific multifunctional Th2 cells
- Increase in peanut-specific regulatory T cells
- Change in peripheral blood transcriptional signatures
- Up and downregulation of distinct gene ontology pathways

Primary Mechanistic Endpoints

- 1. Change in peanut and Ara h 2-specific IgE from baseline as measured by ImmunoCAP assay
- 2. Change in peanut and Ara h 2-specific IgG4 from baseline as measured by ImmunoCAP assay
- 3. Change in peanut epitope-specific IgE and IgG4 binding score from baseline
- 4. Change in basophil activation from baseline, as measured by %CD63+ basophil by flow cytometry/mass cytometry
- 5. Change in frequency of peanut-specific Th2 cells, as measured by CD154 and cytokine co-expression after in vitro stimulation with peanut
- 6. Change in frequency of peanut-specific T cells expressing CD137 and regulatory markers or producing IL-10 after in vitro stimulation with peanut
- 7. Change in peripheral blood transcriptional signature via RNAseq

Secondary mechanistic objectives

Secondary mechanistic objectives are to:

- Determine if immune and transcriptomic measures obtained early in the course of ingestion exposure can predict the development of desensitization or sustained unresponsiveness
- Identify immune and genomic biomarkers of the high threshold phenotype
- (Exploratory) Identify early-appearing functional pathways underlying a successful desensitization course

Secondary Mechanistic Endpoints

- 1. Immune and transcriptomic measures obtained early in the course of ingestion exposure that predict the development of desensitization or sustained unresponsiveness
- 2. Immune and genomic biomarkers of the high threshold phenotype
- **3**. (**Exploratory**) Early-appearing functional pathways underlying a successful desensitization course.

Statistical Analyses

Immunocap Assay: Changes in serum component proteins measured through ImmunoCAP assay will be compared between randomization groups using linear mixed effects models for data collected at baseline, week 16 and the desensitization double-blind, placebo-controlled food challenge visit. The analysis will include a random subject effect and the fixed effect of randomization assignment, time, interaction between randomization assignment and time, and age. Spline models may be considered if the curves exhibit non-linear trends. Values below the limit of detection (LOD) will be imputed as X/sqrt(x)). The linear mixed effects model has the advantage that the estimation of the model parameters will be unbiased even in the presence of missing outcomes, assuming that the missing values depend only on the observed values (missing at random). If the missing at random assumption is not plausible, pattern-mixture modeling (which stratifies subjects by their pattern of missing data) will be used.

Cell population frequency: Quantile-linear mixed effects models will be used for the frequency of %CD63+ basophil, peanut-specific Th2 cells and T cells.

BBEA Assay: The bead-based epitope assay (BBEA) protocol will be used to obtain peanut specific of 64 15-mer epitopes derived from key peanut allergens—34 from Ara h 1, 16 from Ara h 2, and 14 from Ara h. All data processing, quality control, and analyses will be performed in R (version 4.3.3; R Foundation, Vienna, Austria). Binding scores for each epitope in the IgE and IgG4 assays will be obtained via *bbeaR*. Plate effect will be assessed using Principal Variation Component Analysis along with age strata, randomization assignment, visit, the interaction between randomization assignment and visit, and participant. If Plate effect is considered to be large, ie >10% contribution to the variance, Plate will be included as a factor in all analysis. Linear mixed effects models will be fitted by using the *limma* framework– for high dimensional omic data.

Transcriptomic analysis: mRNA libraries will be sequenced on the Illumina HiSeq 4000 System targeting 30 million 150 bp paired-end reads, according to the manufacturer's protocol. The sequencing reads will undergo quality control using FastQC and will be mapped to GRCh38 using STAR v2.4.0g1 aligner. Transcript counts will be estimated using featureCounts. The transcriptome profiles will be filtered to remove low expression genes with cpm \leq 1 in at least 10% of samples using edgeR2. The transcriptome data will be normalized using voom in the limma R package and scaled from -1 to 1. Linear mixed effects models will be fitted for each blood transcript and cell fraction using the lme4 R package. Sex, age, challenge (peanut or placebo), time point (0, 2, 4 hours), reaction threshold (0-5), and interactions between time, challenge, and threshold will be included as fixed effects and a random intercept for each subject.

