### 4.2. Inclusion Criteria

Individuals who meet all of the following criteria are eligible for enrollment as study participants:

- 1. Subject and/or parent guardian must be able to understand and provide informed consent.
- 2. Inclusion criteria for screening DBPCFC: Age 4-14 years, either sex, any race, any ethnicity who are enrolled while strictly avoiding peanut and have a history of sensitization (detectable peanut IgE >0.35 kUA/L).
- 3. Inclusion criteria for randomization (post screening): On screening DBPCFC are able to ingest >=143 mg peanut protein but <5043 mg peanut protein.

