### 4.3. Exclusion Criteria

Individuals who meet any of these criteria are not eligible for enrollment as study participants: [Suggested line items are included in italics; modify, add or remove as needed; line items #1, 10 and 11 should be included without modification]

- 1. Inability or unwillingness of a participant to give written informed consent or comply with study protocol
- 2. Serum peanut-specific IgE antibody level > 50 kUA/L
- 3. Recent (within the past 2 years) life-threatening (grade 3) anaphylactic reaction to peanut.
- 4. Any disorder in which epinephrine is contraindicated such as known hypertension or cardia rhythm disorders.
- 5. History of chronic disease requiring therapy (other than asthma, atopic dermatitis, rhinitis).
- 6. On a build-up phase of any allergen immunotherapy.

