### 13.3 Measures to Minimize Bias

Although this is an open trial, DBPCFCs will be performed by staff blinded to randomization assignment. Randomization will be stratified by age (4-<10 years vs. 10-14 years) and reaction dose at the initial DBPCFC, balanced by blocks of 4 and 6. This will guarantee that both treatment arms have similar distribution of those covariates without pre-specifying a number of patients per strata, which will limit enrollment. Clinical samples for mechanistic studies will be received by the laboratory personnel in coded fashion without indication of intervention allocation.

Defining the timing for the DBPCFC in the control group: Time from randomization to the DBPCFC will be dictated by the achievement of 1 tbsp threshold in children in the intervention group. In order to ensure that the two trial arms will have the same time to DBPCFC on average, we will develop an adaptive algorithm to assign a time to DBPCFC in avoiders that matches that of the consumers. After the baseline DBPCFC, patients in the avoider group will be assigned a 'time to the second DBPCFC' as a value randomly selected from the distribution of the consumer patients with the same baseline reactive dose. Initial distributions for time to DBPCFC will be assumed to follow a uniform distribution centered on the treatment expectations anticipated by the clinicians based on initial DBPCFC (i.e. ~32 weeks for those who fail at 3000 mg, ~72 weeks for those who fail at 300 mg) plus minus 3 weeks. After the recruitment of every 10 patients, the time to OFC distribution for each baseline reactive dose will be updated as a uniform distribution derived from the time to OFC of consumer patients if 2 or more observations are available, otherwise we will keep the initial uniform distribution for that baseline reactive dose. The statistician will receive an email from RedCap alerting them that 10 new patients had been accrued; and will update the timing distributions. Once a patient is randomized to the Avoider group, the unblinded statistician will send the timing of the second DBPCFC to the study coordinator, who will enter the assigned time into RedCap. For monitoring and data checking purposes, the unblinded statistician will maintain their own records. Inconsistencies will be identified and resolved in a timely manner within the monitoring process when producing data inconsistencies and data completeness reports.

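### The epitope models adjust for assay plate only if it exceeds 10% of a total variance that includes between-child variance, so a plate effect that matters for within-child change can go unadjusted

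*SAP*

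**What the plan says.** The rule is in the BBEA Assay paragraph of the SAP Addendum. The plate effect is first measured: "Plate effect will be assessed using Principal Variation Component Analysis". The same decomposition contains age strata, arm, visit, "the interaction between randomization assignment and visit, and participant". Then comes the decision: "If Plate effect is considered to be large, ie >10% contribution to the variance, Plate will be included as a factor in all analysis". The paragraph closes on the model family: "Linear mixed effects models will be fitted by using the *limma* framework". It does not list the fixed and random terms of the epitope models.

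These models serve the third primary mechanistic endpoint: "Change in peanut epitope-specific IgE and IgG4 binding score from baseline".

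On handling of samples, Protocol 13.3 says: "Clinical samples for mechanistic studies will be received by the laboratory personnel in coded fashion without indication of intervention allocation". Neither document describes how samples are assigned to plates. No rule keeps a child's visits together, and none balances arms over plates.

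**The concern.** The yardstick for plate does not match the endpoint. Participant is one of the components, so the 10% is taken of a total that includes between-child variance. A change from baseline removes that component and leaves residual variance, plus plate variance whenever the child's visits sit on different plates. The more the children differ from one another, the smaller plate looks on the SAP's scale, while its weight in the change score stays the same.

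The rule is also one switch for all the epitope analyses (64 epitopes, IgE and IgG4). An epitope with a much larger plate share than the overall figure would go unadjusted with the rest.

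At stake is precision on a primary mechanistic endpoint. The opposite error, including plate when it hardly matters, costs only a few degrees of freedom.

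**Working it through.** **The plan's own figure.** The 10% cut-off is stated without derivation, so there is nothing to reproduce. The question is what the rule lets through.

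**Inputs from the documents.** The 10% rule and the list of components (SAP Addendum, BBEA Assay); change from baseline as the endpoint (SAP Addendum, Primary Mechanistic Endpoints); 36 children per arm (SAP 6.5.1.1); two-sided 5% tests (SAP 6.1).

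**Assumptions, not in the documents.** Participant, plate and residual shares sum to 1, with the other components taken as negligible. The epitope contrast would have 80% power if plate were removed. The participant share is varied because no value is given. The only pointer to it is the entry range of peanut IgE. Protocol 4.2 requires that children "have a history of sensitization (detectable peanut IgE >0.35 kUA/L", and Protocol 4.3 excludes "Serum peanut-specific IgE antibody level > 50 kUA/L". That is a range of about 50/0.35 = 143-fold, which makes a large participant share plausible but does not measure it for epitope scores.

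**Step 1: noise in a change score.** With two visits on different plates, the variance of a change is 2 x (residual + plate) if plate is ignored and 2 x residual if it is removed. Hence

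- SE inflation = sqrt((residual + plate)/residual)
- power = Phi(2.80/inflation - 1.96), where 2.80 = 1.96 + 0.84 is the value for 80% power.

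**Step 2: results for plate shares below the cut-off.**

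| Participant | Plate | Residual | SE inflation | Power |
|---|---|---|---|---|
| 65% | 2% | 33% | sqrt(0.35/0.33) = 1.03 | 78% |
| 70% | 2% | 28% | sqrt(0.30/0.28) = 1.04 | 77% |
| 65% | 5% | 30% | sqrt(0.35/0.30) = 1.08 | 74% |
| 70% | 5% | 25% | sqrt(0.30/0.25) = 1.10 | 72% |
| 65% | 9% | 26% | sqrt(0.35/0.26) = 1.16 | 68% |
| 70% | 9% | 21% | sqrt(0.30/0.21) = 1.20 | 65% |

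**Step 3: dependence on the participant share.** Plate is held at 9.9%, the edge of the rule.

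| Participant | Plate / residual variance | Power, plate ignored |
|---|---|---|
| 0% | 0.099/0.901 = 0.11 | 76% |
| 30% | 0.099/0.601 = 0.16 | 74% |
| 50% | 0.099/0.401 = 0.25 | 71% |
| 70% | 0.099/0.201 = 0.49 | 63% |
| 80% | 0.099/0.101 = 0.98 | 51% |

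Some power is lost even with no between-child variance. A large participant share makes the loss worse but is not needed for it.

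**Step 4: dependence on layout.** Simulation with plate at 9.9% and ignored, two visits, 36 per arm, 4,000 runs per setting, participant share 50/70/80%:

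| Layout | Type I error | Power |
|---|---|---|
| All of a child's visits on one plate | about 5% | 78-79% |
| Samples spread at random over plates | about 5% | 72/64/56% |
| Visits batched separately, arms mixed | about 5% | 72/68/60% |
| Follow-up plates aligned with arm | 38/49/61% | not meaningful |

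In the first layout the plate shift cancels from the child's change. In the third, a shift common to the follow-up plates cancels between the arms, so the contrast is noisier but not biased. Only the fourth gives false positives.

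**Step 5: cost of always including plate.** The addendum does not list visits for this assay. Taking three per randomised child gives 72 x 3 = 216 samples. The 150-200 screened less 72 randomised add 78-128 baseline samples, for a total of 294-344. At an assumed 80 samples per plate that is 4-5 plates, or 3-4 degrees of freedom. The 216 randomised samples alone would need 3 plates, or 2 degrees of freedom.

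**The case against.** The strongest reply is that the rule is a pre-specified numerical threshold on a nuisance component, that plate shares well below 10% do little harm, and that nothing in the documents shows a child's samples being split over plates. Much of this stands. At a 2% plate share the loss is 2-3 points of power, and the 65-68% figure belongs to the edge of the rule. If the laboratory runs each child's visits together, there is almost nothing to repair. The 80% starting power is also hypothetical, since the documents state no power for any epitope contrast.

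A reader might infer more than the documents support:

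- **That most of the variance is known to lie between children.** No variance component or intraclass correlation is given. The 65-70% is an assumption.
- **That the arm comparison is biased whenever visits or arms are unevenly spread over plates.** Uneven visits alone do not bias the arm-by-visit contrast when arms are mixed within plates. Inflated type I error needs plates aligned with arm at follow-up. Coded samples make that unlikely by design, though chance or calendar alignment is not excluded.
- **That deciding from the same data inflates error.** The rule does not select on the treatment contrast, and no inflation from the selection has been shown.

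What the reply does not answer is the mismatch itself. The SAP measures plate against a total that includes variance irrelevant to change, and no stated layout makes up for it.

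**Conclusion.** The point holds as a cheap improvement to one primary mechanistic endpoint. The 10% rule uses a denominator that does not fit a within-child endpoint, so a plate effect that is a material part of the within-child noise can go unadjusted.

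The size depends on two things that the documents do not give. If a child's visits fall on different plates, the fall from 80% power runs from a few points to about 15 points over plate shares of 2-9%, at an assumed participant share of 65-70%. It is about 4 points at a 9.9% plate share with no between-child variance. If a child's visits share a plate, it is negligible. The expected harm is lost precision. A claim of false-positive epitope findings would need evidence that plates line up with arm at follow-up, and there is none. The primary and secondary clinical analyses are not touched.

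**What to change.** Replace the conditional sentence in the BBEA paragraph of the SAP Addendum with wording such as:

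> Plate will be included as a factor in every BBEA epitope model, for IgE and IgG4, whatever its share of the variance. The variance-component analysis will be reported as description only.

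State in advance whether plate is fixed or random. As a fixed factor it costs about 3-4 degrees of freedom at an assumed 80 samples per plate.

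For samples not yet run, add that all visits of a child go on one plate and that arms are balanced across plates. The second part matters because adjustment cannot separate plate from arm-by-visit if the two are confounded; only the layout prevents that. For samples already run, report how arms and visits are distributed over plates, so that a reader can see whether such confounding occurred.

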### AADCRC

The following procedures, assessments, and laboratory measures (windows for sample collection are detailed in the MOP as applicable) will be conducted, some of which to determine participant eligibility for the randomized trial:

- Physical exam, vital signs, complete medical history
- Spirometry (or peak flow under age 7 or if spirometry not allowed per COVID protocols)
- DBPCFC to peanut per modified PRACTALL (and associated examinations)
- Skin prick test to peanut
- Blood samples (before DBPCFC commences and 2 and 4 hours after starting; not to exceed 5cc/kg on a single day or 9.5ml/kg over any eight-week period per NIH guidelines). A saline lock may be placed to facilitate blood sampling at this and other visits where periodic samples are obtained.
- Quality of life survey, diet questionnaire, demographics
- Urine pregnancy if child bearing potential
- Saliva and stool collection

Screening takes place over 3 days (with one DBPCFC per day for 2 days). Each day is 4-8 hours.

If a participant reacts during the placebo arm of a DBPCFC, the DBPCFC may be repeated once. If a determination of reaction cannot be made due to unwillingness to repeat the DBPCFC or repeated placebo reactions, participation will end and any associated data will not be included in the analyses.

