6. STATISTICAL METHODOLOGY

6.1 General Principles

Continuous variables will be summarized using the following descriptive statistics: number of non-missing values, means, standard deviations, medians, interquartile range, maximum, and minimum. Categorical variables will be summarized using number of non-missing values, counts and percentages.

For any variable measured at multiple points in time, change from baseline will be calculated as the difference between the value of the variable at a specific point in time (e.g. 1 year) minus the baseline value. Relative change from baseline will be calculated as the value of a parameter at a specific point in time minus the baseline value of the parameter divided by the baseline value of the parameter. Percent change will be calculated as the relative change multiplied by 100.

All hypothesis testing will be conducted at the 0.05 two-sided significance level unless otherwise specified. P-values will be rounded to three decimal places. P-values less than 0.001 will be reported as <0.001 in tables. P-values greater than 0.999 will be reported as >0.999.

Should any of the statistical methods proposed prove unsuitable during data analysis, more appropriate methods will be used. These include data transformation (for example to a logarithmic scale) to satisfy model assumptions such as normally distributed residuals with constant variance, the application of non-parametric techniques or the use of a different link function or modeling technique.

Additional ad-hoc analyses may be conducted as deemed appropriate.

All analyses will be conducted using SAS V9.4 or higher and R statistical software (version 4.2.2 or higher).

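### As worded, the RNA-seq expression filter keeps only genes above 1 cpm in more than 90% of samples, so a gene silent at rest and expressed only after peanut is always removed

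*SAP*

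**What the plan says.** The filter is in the SAP addendum, under Statistical Analyses, in the paragraph on transcriptomic analysis: "The transcriptome profiles will be filtered to remove low expression genes with cpm" followed by a less-than-or-equal sign and "1 in at least 10% of samples using edgeR2".

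The same paragraph then describes a mixed model for each transcript. Among its terms are "challenge (peanut or placebo), time point (0, 2, 4 hours), reaction threshold (0-5"). The model also carries their product terms, since the sentence goes on to say that "interactions between time, challenge, and threshold will be included as fixed effects". The sampling times agree with Protocol 8.2, which lists "Blood samples (before DBPCFC commences and 2 and 4 hours after starting", with the two challenge days held separately. Protocol 8.3 repeats the 0, 2 and 4 hour draws at the desensitization and sustained unresponsiveness challenges.

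Change in the blood transcriptional signature is the seventh primary mechanistic endpoint (Protocol 3.2.2 and the SAP addendum). Neither document gives another version of the filter or an exception for genes expressed under one condition only.

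**The concern.** Expression filters of this kind normally keep a gene if it is clearly expressed in some minimum share of samples, so that a gene active in only one condition survives. This sentence does the reverse: a gene is discarded if it is low in a small share of samples. In a design that compares conditions, being low in some conditions and high in others is the pattern that the model is meant to detect.

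The interactions between time, challenge and threshold are the terms that would show expression changing after peanut but not after placebo, or differently by threshold. If the filter is coded literally, the genes with the sharpest contrast of this kind (off at rest, on after peanut) never reach the model. An analyst who instead codes the usual rule departs from the written plan without a record of it.

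**Working it through.** The documents state no figure for this filter, so there is nothing to reproduce. The check is a count of samples.

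**Inputs.**
- Removal rule: cpm at or below 1 in at least 10% of samples (SAP addendum).
- Samples per child per challenge visit: 2 challenges × 3 times = 6 (SAP addendum; draw times in Protocol 8.2).
- Samples taken after peanut: 2 of the 6 (2 and 4 hours on the peanut day).
- Share of children in whom the gene is induced, r: not given. A range of 30% to 100% is assumed.

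**Rule restated.** A gene is kept only if fewer than 10% of samples are at or below 1 cpm, that is, if more than 90% are above it.

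**Gene off at rest and on at both post-peanut times.** Share of samples on = r × 2/6; share off = 1 − r × 2/6.

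| r | On | Off | Rule as worded (remove if off ≥10%) | Reversed rule (keep if on ≥10%) |
|---|---|---|---|---|
| 100% | 33.3% | 66.7% | removed | kept |
| 70% | 23.3% | 76.7% | removed | kept |
| 50% | 16.7% | 83.3% | removed | kept |
| 30% | 10.0% | 90.0% | removed | exactly at the limit |

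The result under the rule as worded does not depend on r, because the placebo-day samples and the peanut-day 0-hour sample alone make up 4/6 = 66.7% of the set. With 150 children (the lower end of the screening target) and one challenge visit each, there are 150 × 6 = 900 samples. Ninety low samples suffice for removal, and such a gene has at least 150 × 4 = 600.

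**Robustness.** If only peanut-day samples were filtered, the 0-hour sample would still be off, 1/3 = 33% of the set, and the gene would still be removed. Reading the sign as strictly less than 1 makes no material difference.

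**Other patterns lost under the rule as worded.** A gene on in all three peanut-day samples of every child is off in 3/6 = 50% and is removed. A gene above 1 cpm at rest that falls to 1 cpm or below at both post-peanut times is removed once r × 2/6 ≥ 10%, that is, r ≥ 30%. A gene silent throughout one threshold group is removed if that group supplies 10% or more of the samples.

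**Does reversing the rule suffice?** A gene on at both post-peanut times is kept once r ≥ 0.10/(2/6) = 30%. A gene on at one post-peanut time is kept once r ≥ 0.10/(1/6) = 60%. If the six threshold levels (0–5) were of equal size (an assumption), a gene induced in one level only would be on in 1/6 × 2/6 = 5.6% of samples and would still be dropped. Under a smallest-group rule with the same equal sizes and 900 samples, each of the 2 × 3 × 6 = 36 cells holds 900/36 = 25 samples. That gene is on in 2 × 25 = 50 and is kept.

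**The case against.** The strongest reply is that this is a drafting slip. The stated purpose is to remove genes with low expression, and a rule that removes a gene for being low in a tenth of samples does not fit that purpose well. The same addendum has other slips, such as an undefined expression for values below the detection limit and an allergen name left incomplete. The working code may well use the usual rule. This stands as an explanation, but it does not correct the text: the sentence has one plain reading, and nothing else in the documents replaces it.

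A second reply concerns the extent of the harm. A reader might infer that the filter deletes reaction-induced genes in general. The documents do not support that. Only genes resting at or below 1 cpm are affected, and those induced from a higher level pass. Acute induction is also one aim among several: Protocol 13.1 names resting-state differences between high- and low-threshold children as well. The 67% describes the sample count for one type of gene, not a share of the transcriptome.

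A reader might also take SAP 6.1, "All hypothesis testing will be conducted at the 0.05 two-sided significance level unless otherwise specified", to mean that every transcript and epitope will be declared significant at an unadjusted 0.05. For the 64 epitopes and two isotypes that would imply 64 × 2 × 0.05 = 6.4 false positives per contrast under the null. This reading does not hold. The SAP's opening paragraph says that the main plan leaves the mechanistic objectives out of scope, and the addendum nowhere says that unadjusted p-values will be reported. What remains is a missing detail: the addendum names no error-rate method for the epitopes or the transcripts.

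**Conclusion.** The point holds for the filter as written. Any gene at or below 1 cpm at rest and expressed only after peanut is off in at least 67% of the modelled samples, far beyond the 10% that triggers removal, whatever share of children react. The count assumes that the filter runs over the samples named in the model, in roughly equal numbers per condition; restricting it to peanut-day samples does not change the outcome.

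The number of genes lost cannot be estimated from the documents. The consequence is confined to the RNA-seq work (one primary mechanistic endpoint and the related secondary ones) and does not touch the clinical primary or secondary analyses. The wording is probably an inversion, so this is a correction to make before the analysis, not evidence that the analysis has been or will be run wrongly.

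**What to change.** Restate the filter as a retention rule, for example: *genes with cpm >1 in at least 10% of samples will be retained*. To protect genes induced in only one threshold group, set the minimum number of samples to the size of the smallest challenge-by-time-by-threshold group instead. State also which samples the filter runs over.

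The cost is one or two sentences and no new data. More low-count genes will enter the models, and the smallest-group version admits more of them if one threshold group is very small. As a separate note, the addendum could name the error-rate method for the 64 epitopes and the transcripts; the filter correction does not depend on it.
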